## PROTOCOL SUMMARY

TITLE	:	C-TRIUMPh: Cohort for TB Research by the Indo-US Medical Partnership
DESIGN	:	Multi-centric Prospective Observational Study
POPULATION	:	
 
(i) Active TB Cohort (Cohort A): 1200 adults and children with active TB (800 adults with newly diagnosed PTB starting Category I Rx (85% being AFB smear or Gene Xpert positive) + 200 adults with EPTB +200 children with TB)
 
(ii) Household (HH) Contact Cohort (Cohort B): 3200 adult and children -house hold contacts of the adults with active PTB
 
(iii) Control Cohort (Cohort C): 300 adults and 200 children – without a h/o of known TB contact100 households.
 
 
Each site will enroll approximately 50% of the sample

STUDY SITES	:	
 
(i) National Institute for Research in Tuberculosis (NIRT), Chennai
 
(ii) Byramjee Jeejeebhoy Medical College CTU (BJMC), Pune
 

FOLLOW UP DURATION	:	
 
(i) Active TB Cohort: Each participant will be followed up for 24 months
 
(ii) Household Contacts cohort: Each participant will be followed up for 24 months
 
(iii) Control Cohort: Each participant will be followed up for 12 months
 
 
C-TRIUMPh will undertake both epidemiologic/clinical and basic laboratory research studies that will address three specific aims -
 
Aim 1: To measure the host and microbial factors associated with TB treatment outcomes in Indian adults and children (Active TB cohort)
 
Aim 2: To investigate the host and microbial factors associated with progression from infection to active TB disease in adults and children. (Household Contacts)
 
Aim 3: To explore the host and microbial factors associated with TB transmission. (Household Contacts and Control Cohorts)

OBJECTIVES	:	

## 2. BACKGROUND INFORMATION AND SCIENTIFIC RATIONALE

### 2.1. INTRODUCTION

India has the world's highest burden of TB. An estimated 2 billion are MTB infected, 9 million develop active TB disease each year, resulting in 1.7 million deaths. Left untreated, each person with active TB will infect on average 10-15 people every year. India, with 40% of its 1.2 billion populations latently infected with MTB and 2.3 million developing active TB disease each year, accounts for 26% of the world's entire burden of TB. In addition, an estimated 99,000 active TB cases are drug-resistant TB (MDR and XDR TB) and recently India became the third country to report totally drug resistant TB (TDR) [1]. TB places a huge economic burden in India with direct and indirect costs estimated at \$23.7 billion annually.

### 2.2. FACTORS ASSOCIATED WITH POOR TB TREATMENT OUTCOMES

Relative impact of potentially modifiable host factors (e.g. HIV, DM, smoking, IAP, alcohol misuse, under-nutrition, mental health status) on treatment outcomes such as failure, recurrence or death is not well established in populations including Indians. While most patients treated for TB are cured of TB, poor outcomes such as treatment failure, recurrent disease and death remain important challenges. Approximately 85% of Indian patients who are treated for active smear-positive PTB via the Directly Observed Therapy Strategy (DOTS) are cured (AFB smear and culture negative). However, 2% fail (remain smear positive at 5 months of treatment), 6% die on treatment, and the remainder default or transfer out. Furthermore, approximately 12% of cured patients develop recurrent TB within 18 months of treatment, either due to relapse of the same strain or re-infection from others in the community. A patient's second course of TB treatment is more than twice as likely to fail, and more than 4 times as likely to involve MDR-TB. As shown in *Table 1*, poor treatment outcomes are linked to potentially modifiable host factors though with variable quality of evidence and estimations of individual contributions.

**HIV** has clearly been shown to increase TB treatment failure, death and recurrence and low CD4 counts increase that risk further [2,3]. While HIV is an important risk factor at the individual level, it is not likely to be a primary driver of poor treatment outcomes in India's TB epidemic as only 0.3% of India's population has HIV and only 2-15% of Indian patients with TB have HIV co-infection.

Though **Diabetes Mellitus (DM)** increases risk of TB two-fold compared to 22 times for HIV, DM is estimated to account for at least 20% of smear positive PTB cases in India [4-6], making it a more relevant risk factor in this setting. Most but not all data suggest that DM is associated with reduced 2-3 month sputum conversion, increased mortality (pooled RR of 1.89 based on 23 studies) [7] and may be a risk factor for TB recurrence and relapse (RR of 3.89) [7] but few studies have adjusted appropriately for confounders. It is unknown if DM is associated with acquired drug resistance.

In India 44% currently use **tobacco** (11% smoke, 33% use smokeless tobacco), and 70% of rural Indians and 20% of urban Indians are exposed to indoor air pollution (IAP), which results from burning of biomass fuels such as wood and cow dung) [8,9]. Despite heterogeneity in population based data, meta-analyses indicate that tobacco smoking is associated with TB disease severity and TB-related mortality; one Indian study demonstrated 50% of TB deaths were due to smoking.[10,11] Tobacco smoke alters T cell responses, modulates mycobacterial containment, and impairs macrophage cytokine responses [12,13] and nicotine itself has systemic immunomodulatory impact and therefore smokeless tobacco may be associated with adverse TB treatment outcomes. IAP exposure generates particulate matter, carbon monoxide, and numerous other potentially toxic compounds like polycyclic aromatic hydrocarbons (PAHs) [14].Furthermore, IAP like tobacco smoke, interferes with mucociliary clearance, decreases several antibacterial properties of lung macrophages such as adherence and phagocytic rate, and has been associated with poor lung health (e.g. COPD/ bronchitis, asthma exacerbations)[14]. While there is a biological plausibility to suggest a link between tobacco, IAP exposure and TB, few studies to date have adequately measured these exposures and prospectively assessed their relationship to TB treatment outcomes, while accounting for important confounders like alcohol.

Many other factors may affect TB treatment outcome. In India, rates of alcohol use is on the rise, and 50% of adults and children are undernourished (low BMI or low weight-for-age), 30% are estimated to be vitamin D deficient, 6% depressed, and 20% food insecure [15, 16].**Alcohol**, particularly heavy alcohol use, directly and indirectly impairs the cell-mediated immunity and macrophage functions which are essential for host response to TB [17]. Alcohol use also impairs **TB treatment adherence** and causes micro- (i.e. Vitamin deficiencies) and macronutrient malnutrition (e.g. **low BMI**), which independent of alcohol use, have been negatively associated with TB immunity [18]. Moreover, deficiency of Vitamin D may cause reduced sputum smear conversion and increased inflammation during TB treatment [19]. Low BMI has been associated with treatment failure, death and recurrence [17, 20]. It is unknown what role other nutritional deficiencies or household (HH) **food insecurity** play in TB treatment outcomes. **Mental Health** status, particularly depression, may also influence treatment adherence and reduce immunity [17, 21, 22].Therefore, careful ascertainment of alcohol, treatment adherence, nutrition status, HH food insecurity and depression is critical.

While non-adherence and **suboptimal plasma concentrations of anti-TB medications** are also likely contribute to poor TB treatment outcomes, target concentrations of first-line TB drugs are based on relatively limited evidence [23-26]. Importantly, treatment outcomes differ by geographical setting, complicating evaluation of relationships between concentration-effect relationships for TB drugs [27]. In India, for example, slow INH metabolizer genotype is common, so, theoretically, low INH concentrations may be relatively uncommon; however, malnutrition and DM are common and can lead to low rifampicin concentrations [28]. Furthermore, there are few studies evaluating the evolution of drug resistance among individual patients and the relationship between drug exposure and acquired resistance [29]. Many **socio-behavioral factors** influence drug adherence too - stigma, mental health, literacy, social support, substance abuse etc. – and, thereby, influence drug exposures.

Non-modifiable host factors like age, sex, human genetic polymorphisms, novel proteins and microbial factors (e.g., mycobacterial strain types) are also likely to influence TB treatment outcomes. Human genetic variants (such as that of leukotriene A4 hydrolase-*LTA4H*) [30, 31] may impact treatment outcomes. Animal model studies have also identified peptidoglycan recognition proteins (PGYRP1-4) [32-34] and nucleotide binding oligomerization domain-containing proteins (NOD1, NOD2) [35, 36] are directly bactericidal against many gram positive and gram negative bacteria. NOD2 has been shown to be involved with detection and defense response to MTB but the role of the others in TB is unknown. Thus the prevalence of *LTA4H* or expression of PGYRP or NOD proteins may differ between persons who have non-relapsing cure versus those who do not but this needs further investigation. There is also mounting evidence that MTB has more sequence variation than previously estimated and that some of this genetic diversity may actually have important clinical phenotypic sequelae [37].

Animal studies have shown that MTB strains can differ in virulence and immunogenicity [38]. For example guinea pig studies from the early 20th century observed that MTB strains from Indian TB patients were less virulent than strains from United Kingdom patients [37]. Beijing genotype MTB strains are linked to increased likelihood of AFB sputum smear positivity [37]. Therefore, strain types may influence treatment outcomes, the ability to cause disease and to transmit within certain geographic settings or ethnic groups [39].

### **2.3. FACTORS ASSOCIATED WITH PROGRESSION TO ACTIVE TB DISEASE**

Many of the above-mentioned potentially modifiable factors have been associated with progression to active TB, but their relative independent and combined contributions towards risk of active TB disease has not been well studied, particularly in India. HIV increases the risk of reactivation of latent MTB infection by up to 100 times and increases the risk of progression to active disease in those who acquire new MTB infection [40]. Other less potent but more common risk factors including DM, under nutrition, smoking and alcohol misuse have been associated with 2-3 times increased risk of development of active TB [41- 43].

Non-modifiable host factors such as age, sex, and host genetics may also be influential. Disease risk after primary infection is highest in children < 4 years, then decreases until age 10, after which a second peak starts and is noted through reproductive age until 34 years in women but is more sustained in men until age of 50 years [44]. These age- and sex-specific differences also impact the presentation of disease where young children are more likely to have disseminated disease while women are more likely than men to have EPTB. The mechanisms for these differences are unknown. Host genetic polymorphisms and host proteins may also be associated with risk of developing active TB, [45, 46] but it is unknown what the prevalence or association is of LTR4 genetic variants or PGYRP or NOD proteins with risk for developing active TB. Microbial strain lineage may also matter. A study among Gambian TB patients and their household contacts found that progression to active TB but not transmission varied by MTB lineage with *M.africanum* causing lower proportion of active TB disease than other MT strains [38]. Further,

strain lineage has differing phylogeography, where India, sub-Saharan Africa and the Americas each have different predominant strain lineages [37]

#### **2.4. FACTORS ASSOCIATED WITH TB ACQUISITION AND TRANSMISSION**

There is a variable response to exposure to infection. Many of the same host and microbial factors described above are associated with transmission of infection, but may have different relative contributions (**Table 1**). In addition, proximity to the index case, characteristics of the HH and duration of exposure are important. Host genetics may also play a role. Further, MTB transmission dynamics appear to vary by MTB strain type as demonstrated by Albanna et al [47] who found that east African Indian MTB strains were associated with reduced transmissibility compared to other MT lineages.

#### **2.5. MULTIPLE HOST AND MICROBIAL FACTORS ARE LINKED TO TB TREATMENT OUTCOMES, PROGRESSION AND TRANSMISSION**

While the quality and strength of the evidence varies substantially, implicated *host factors* include social (e.g. residence in crowded urban setting, low socioeconomic status), environmental (e.g. IAP), and clinical/biological (e.g. age, sex, co-morbidities such as HIV, DM, tobacco, alcohol, malnutrition, depression, genetics) determinants. *Microbial factors* include strain type (e.g. Beijing vs. other), drug-resistance pattern, as well as genes and proteins associated with virulence, persistence, and evasion of host immune responses. Treatment outcomes are also impacted by drug adherence and serum concentrations of TB drugs, which in turn are influenced by many of the above-mentioned host related factors.

#### **2.6. NEED FOR C-TRIUMPH STUDY**

Studies to date have not included a prospective comprehensive assessment of these multiple host and microbial factors to accurately examine their independent and combined attributable impact on outcomes of TB treatment, progression and recurrence, and transmission. Since short-term microbiologic outcomes (like 2-month sputum culture conversion to negative) correlate poorly with long-term treatment outcomes (cure without relapse), a prospective cohort that follows patients for at least 18 months post-treatment is recommended to assess clinically-relevant treatment effects.

Understanding the relative importance of potentially modifiable and non-modifiable factors will help to inform which of them should be prioritized for public health interventions to reduce the burden of TB in India and other settings. We will also be able to provide much needed data on interaction and combined risk of these factors which can be used for improved TB epidemic modeling. Establishing a specimen repository for host and microbial studies, archiving MTB strains from prevalent and incident TB cases will allow for molecular epidemiological typing and further exploration of associations between MTB strain type and clinical phenotypes such as progression to active TB. These MTB strain libraries are also valuable for future selection of novel targets for mycobacterial diagnostic tests and TB vaccine development

### 3. Objectives

The study will establish and maintain 3 prospective cohorts -- adults and children with active TB disease (**1.Active TB Cohort**), adults and children at high risk for developing active TB (**2.Household Contacts Cohort**), and adult and children controls who do not have any known exposure to TB (**3. Control Cohort**) to address our 3 specific aims-

**Aim 1:** To measure the host and microbial factors associated with treatment outcomes in Indian adults and children

**Aim 2:** To investigate the host & microbial factors associated with progression from infection to active TB disease in Indian adults and children

**Aim 3:** To explore the host and microbial factors associated with MTB transmission

**TABLE 1. C-TRIUMPH – STUDY OBJECTIVES AND TIMEFRAME**

KEY OVERARCHING SCIENTIFIC QUESTIONS				
HOST FACTORS		MICROBIAL FACTORS		
Which host factors, individually or combined, are associated with TB treatment outcomes, disease progression and transmission in India?		Which microbial factors, individually or combined, are associated with TB treatment outcomes, disease progression and transmission in India?		
SCIENTIFIC HYPOTHESES				
H0 Potentially modifiable (HIV, DM, tobacco, IAP, alcohol, undernutrition) and non-modifiable host factors (age, sex, genetics) alone or in combination have the greatest association with TB treatment outcome, disease progression and transmission in India		H0 Specific Mtb strain lineages and drug susceptibility patterns are most highly associated with TB treatment outcome, disease progression and transmission in India		
PRIORITY RESEARCH STUDIES				
Clinical/Epi Studies		Lab Studies	Clinical/Epi Studies	Lab Studies
Specific Aim 1 Treatment Outcome	1. Prevalence and relative contributions of HIV, DM, tobacco, IAP and other modifiable risk factors on TB treatment outcome (Year 2-4) 2. Population PK of first line TB drugs, factors associated with their concentrations (NAT2, SLCO1B1 genotype, BMI, DM, HIV, etc), and treatment outcome (Year 3,4) 3. Hair samples to measure PK of first line TB drugs and correlate with drug adherence and plasma drug concentrations (Year 2-4)	1. Functional genetic variants in Indian populations within LTA4H and other components of eicosanoid and TNF pathways and associations with treatment outcomes (Years 4,5) 2. Whole blood transcriptome, proteosome, clinical presentation (Year 3) and treatment outcome (Year4) 3. Differential expression of PGLYR and NOD proteins in active TB (Year 3)	1 Mtb strain lineage, drug susceptibility, clinical presentation (Year 3) and treatment outcome (Year 5)	1. Transcriptome and lipid profile of serial Mtb strains from patients on treatment (Years 3,4) 2. Whole genome sequencing to assess microbial genes associated with PTB vs CNS TB in adults and children (Years 4,5)
Specific Aim 2 Disease Progression	1. Host markers of inflammation, oxidative stress, IAP, nicotine and risk of development of active TB (Year 3) 2. Impact of HIV, DM, tobacco, IAP and other modifiable risk factors on development of active TB (Year 5) 3. Estimate risk of disease progression by TST/QGIT status in adults and children (Year4,5)	1. Biosignatures of latency and active TB (Year3,4) 2. Host response to 16 novel Mtb antigens for diagnosis of LTBI and active TB (Year 3,4) 3. Differential expression of PGLYR and NOD proteins in different stages of infection (Year 3,4)	1. Compare index Mtb and HH incident TB strains to determine if specific Mtb strain types are associated with development of active TB (Years 4,5)	1. Microbial transcriptomebiosignatures associated with progression to active disease (Years 3,4)
Specific Aim 3 Transmission	1. Within HH transmission dynamics (Year 4,5) 2. Relative contribution of HIV, DM, smoking, IAP and other modifiable risk factors on TB transmission(Year 5)	1. Host sputum and peripheral blood inflammation markers, sputum macrophage function, in IAP and/or tobacco exposed and risk of increased host susceptibility (Years 3,4)	1. Compare Mtb strain sequences and drug susceptibility patterns of transmitters vsnontransmitters(Years 4,5)	1. Microbial transcriptomebiosignatures associated with transmission of Mtb infection (Years 3,4)

## 4. STUDY DESIGN

- 4.1. STUDY TYPE Multi-centric Prospective Observational Study
- 4.2. STUDY DURATION 5 years
- 4.3. STUDY POPULATION 3 prospective cohorts - Active TB, HH Contacts and Controls will be established
- i. **ACTIVE TB COHORT** will include adults with newly diagnosed active pulmonary TB (PTB) starting RNTCP Category I treatment (with at least 85% being AFB smear or GeneXpert positive at entry), adults with extrapulmonary TB (EPTB), and children with TB.
  - ii. A **HH contact** will include all adults and children living in the same house as the adult (>18 yrs) active PTB participant during the 3 months prior to diagnosis of TB
  - iii. **CONTROL HHS** will be randomly selected from within a 5km radius of the Index case HH.
- 4.4. STUDY SITES
- NIRT Chennai* –The NIRT clinical site will be enrolling cohort patients attending RNTCP clinics at the primary health centers (PHCs) of 2 selected Tuberculosis units (TU) in Tiruvallur district. There are 6 TB units (TU) in Tiruvallur district. For the proposed Active TB cohort, we will enroll TB patients attending 2 of these TU's namely Velliyur and Poonamalle TU's.
- BJMC Pune* – The BJMC site will be enrolling cohort patients attending RNTCP clinics at BJ Medical College and the referrals from the other DOT centre's in the city. There are two potential sources for identifying new active TB cases at BJMC. These include the BJMC RNTCP outpatient clinic (OPD), which receives referrals from the community as well as from other OPD's at BJMC where patients with TB present, including the BJMC NACO HIV ART Centre (the largest HIV treatment centre in Pune); the antenatal clinic and paediatric clinics. TB patients will also be identified following admission to the inpatient wards (adult, antenatal and paediatric).

## 5. STUDY POPULATION

### 5.1. RATIONALE FOR SELECTION OF STUDY SUBJECTS

Each of the 3 Cohorts will establish a clinical database, including socio-behavioral assessments, as well as a strategic specimen repository of samples obtained from baseline and selected follow-up time points. MTB isolates from confirmed TB cases will also be stored.

- i. Active TB cohort will be used to address Aim 1 (To examine the host and microbial factors associated with TB treatment outcomes in Indian adults and children) and Aim 3 (To explore the host and microbial factors associated with MTB transmission).
- ii. The HH Contact Cohort will be used to address Aim 2 (to investigate the host and microbial factors associated with the progression from infection to active TB disease in Indian adults and children) and Aim 3.
- iii. The Control Cohort will be used in conjunction with the Active TB and HH Contact Cohorts to undertake exploratory studies focused on biomarker discovery for predicting progression to active disease and transmission by creating a comparison group that is similar to the active and HH contact cohorts in terms of geography and its attendant co-factors (e.g., SES).

### 5.2. SUBJECT INCLUSION CRITERIA

#### ACTIVE TB COHORT (ALL MUST APPLY)

- i. Adults and children (<14 years of age) with newly diagnosed PTB; or EPTB presenting to Velliyur and Poonamalle TUs, in Tiruvallur and the BJMC RNTCP that meet RNTCP Cat-1 treatment criteria;
- ii. Ability of participant/legal guardian to provide informed consent/assent;
- iii. Allow home visits;
- iv. Live within a 50km radius of either of the 2TU's or the BJMC RNTCP and plan to remain in the area for the duration of the study.

**Note:** Consenting HH contacts from HH contact cohort with newly diagnosed PTB or EPTB who meet the inclusion criteria for Active TB Cohort may be eligible for enrollment into the Cohort A.

PTB will be either smear or Xpert-positive at entry; or smear negative at entry but culture confirmed by 12 weeks.

**Note:** Adult patients with PTB who are enrolled but found later to have a negative sputum culture for MTB will be followed up in the study. Feasibility of follow-up will be reviewed if the proportion of smear +ve but culture -ve cases account for 5% of total sample size (or approximately 20 participants per site).

**HOUSEHOLD CONTACTS COHORT (ALL MUST APPLY)**

- i. All adults and children living in the same house as the adult (>18yrs) active Pulmonary TB participant during the 3 months prior to diagnosis of TB.
- ii. Ability of participant/legal guardian to provide informed consent/assent

**CONTROL COHORT (ALL MUST APPLY)**

- i. Individuals with no know prior exposure to MTB
- ii. Living within a 5km radius of HH contacts
- iii. Ability of participant/legal guardian to perform informed consent/assent

**5.3. SUBJECT EXCLUSION CRITERIA****ACTIVE TB COHORT**

- i. Critical illness where life expectancy is < 1 month
- ii. Children weighing less than 5kgs
- iii. Presence of a medical condition that, in the investigator's opinion, would interfere with the individual's participation or interpretation of results
- iv. Received > 1 week (five daily or 3 intermittent doses) of multi-drug TB therapy in the preceding 30 days
- v. Received more than seven days of fluoroquinolone therapy or other drugs with anti-TB activity (e.g., rifampicin, ethambutol, clofazamine, aminoglycosides) for any reason in the preceding 30 days
- vi. Failure to provide consent for enrolling HH contacts

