## 6. STUDY PROCEDURES

### 6.1. SCREENING

#### Recruitment of Active TB Cohort

A study counselor or nurse will determine if each patient identified at the two study sites, meets the inclusion criteria for the Active TB Cohort study. Patients who fulfill the inclusion criteria will be invited to participate in the Active TB Cohort. Details of the study, including study objectives and outcomes, will be explained to the patients in their native language and they will be asked to provide informed written consent prior to initiation of screening procedures. Informed consent of legal guardians and assent of the child will be obtained for participants under the age of 18 years. All participants will also be asked to provide home visit consent and agree to reveal their TB status to family members for the potential recruitment of participants for the Household Contacts Cohort. The timing of all follow up visits for the study participant from Cohort A is timed from the initiation of their TB treatment

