#### Recruitment of Household Contact Cohort

An outreach team (eg- clinician, counselor and field investigator) will approach all participants enrolled in the Active TB Cohort for the potential enrollment of family members in the Household Contact Cohort. A household contact investigation among its members will be conducted only if the index case of the household had consented to the home visit and enrolment of their family members into the study. Enrollment of a household contact will occur within two weeks to 2months of the index case from Cohort A. Individual household members will be consented for the study procedures at the initial visit at their homes. The RNTCP nurse, PHC staff or the DOTS provider who supervises the TB treatment of the index case will support and participate in community education and awareness of the study and in recruitment of household contacts of the index case. A trained outreach team comprised of a study physician, nurse and counselor will go to the home to consent patients.

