## 9. STATISTICAL CONSIDERATIONS

### 9.1. SAMPLE SIZE AND ANALYSIS PLAN

**Aim 1.** The Active TB Cohort will include 800 adult PTB cases, 200 adult EPTB cases and 200 pediatric TB cases. The primary analysis set will be 800 adult PTB patients. Secondary analysis sets will include EPTB and pediatric TB.

Primary outcome is poor treatment outcome defined as failure, recurrence or death. Secondary outcomes will include time to AFB smear negativity, time to sputum culture negativity; time to detection of MGIT positivity. Host factors age, sex, DM, HIV, IAP exposure, tobacco exposure, malnutrition, and mental health will be key predictors for poor treatment outcomes.

Person-years of follow-up will be calculated for each member of the analysis set. Of TB patients who experience the outcome of interest, person-years of follow-up will be calculated as number of years between date of enrollment and date of event. Among those without the outcome person-years will be the number of years between enrollment and last date of follow-up. Crude treatment failure rates and 95% exact Poisson confidence intervals in the presence and absence of primary risk factors will be calculated. Adjusted treatment failure rate ratios will be estimated using multivariate Poisson regression models with person-years of follow-up as an offset. The Poisson regression models will also investigate interaction between individual and HH factors that might influence treatment outcomes.

A secondary subgroup analysis (may not be sufficiently powered) by enrollment sites, NIRT and BJMC, will be performed by adjusting the level of significance using a Bonferroni adjustment.

**Aim1 Power.** For Aim 1, we expect 20% (n=160) of 800 adult PTB cases will have the composite primary outcome (2% will fail, 6% will die, and 12% will have recurrence). This study will have at least 90% power at 5% level of significance to identify host and microbial risk factors (enumerated in section 3B3), with a prevalence of 10% - 40%, associated with poor treatment outcomes with relative risk ratio ranging from 1.5 to 6.0 over 24 months of follow-up.

**Aim 2.** The analysis set is individuals in the HH Contact Cohort: 3200 HH contacts of 800 PTB patients.

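### The household-consent exclusion covers the whole Active TB Cohort, although only adult pulmonary cases can be index cases for the Household Contacts Cohort

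*Protocol*

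**What the plan says.** Section 5.3, Active TB Cohort, item vi, excludes for "Failure to provide consent for enrolling HH contacts". The item stands in the list for the whole cohort and has no qualifier. Section 6.1 (Recruitment of Active TB Cohort) asks all participants for home-visit consent and to "agree to reveal their TB status to family members for the potential recruitment of participants for the Household Contacts Cohort". Section 5.2, item iii for the same cohort, also requires that home visits be allowed.

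Section 6.1 (Recruitment of Household Contact Cohort) says that the outreach team "will approach all participants enrolled in the Active TB Cohort for the potential enrollment of family members", and that a contact investigation takes place "only if the index case of the household had consented to the home visit and enrolment of their family members into the study".

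Cohort B is narrower. Section 5.2 admits people "living in the same house as the adult (>18yrs) active Pulmonary TB participant" in the three months before diagnosis. Section 4.3 has the same limit ("living in the same house as the adult (>18 yrs) active PTB participant"), and the Protocol Summary also draws the contacts from adults with active PTB.

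On numbers, section 9.1 states: "The Active TB Cohort will include 800 adult PTB cases, 200 adult EPTB cases and 200 pediatric TB cases". The Aim 1 primary analysis set is the 800 adult PTB patients, with EPTB and paediatric TB as secondary sets. The Aim 2 set is 3200 contacts of 800 PTB patients, and the Aim 3 set is the household members of index PTB cases.

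**The concern.** The sections describe different index populations. The exclusion, the disclosure request and the outreach instruction treat every Cohort A participant as a potential index case. The Cohort B definition, its sample size and the Aim 2 and Aim 3 analysis sets recognise only adult PTB cases.

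Two things are at stake. The first is accrual: a site that follows section 5.3 literally refuses an otherwise eligible EPTB adult, or a child, over consent to a cohort which that case cannot feed. The second is selection: those who remain are people willing to involve the household. Section 2.2 names stigma, mental health and social support as influences on adherence, and section 9.1 makes HIV and mental health key predictors of poor outcome. If willingness to disclose is related to these factors, the EPTB and paediatric sets are selected on something close to the predictors under study. For adult PTB patients that price buys contacts for Cohort B. For the other two groups it buys none.

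**Working it through.** **Inputs.** Cohort A is 800 adult PTB, 200 adult EPTB and 200 children (section 9.1), with a total of 1200 (Protocol Summary). Cohort B is 3200 contacts of 800 PTB patients (section 9.1). The biosample subset is 200 households with 800 contacts (section 6.2, Table 2, footnote 7).

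**Step 1. The plan's own totals.** 800 + 200 + 200 = 1200, which reproduces the stated size of Cohort A.

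**Step 2. Which households Cohort B was sized on.**
- Adult PTB cases only: 3200 / 800 = 4.0 contacts per household.
- All adult cases: 3200 / 1000 = 3.2.
- All of Cohort A: 3200 / 1200 = 2.67.

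The biosample subset gives 800 / 200 = 4.0, which agrees with the first line only. The Aim 2 power paragraph divides the contacts into 85% (2720) of smear-positive and 15% (480) of smear-negative PTB cases. 2720 + 480 = 3200, so no planned contact is left for an EPTB or paediatric index case.

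**Step 3. Share of Cohort A covered by the rule but unable to serve as index.** (200 + 200) / 1200 = 400 / 1200 = 33.3%. Adult EPTB alone is 200 / 1200 = 16.7%. PTB participants aged 14 to 18, if any are enrolled, would also fail the age limit for an index case. Their number is not given.

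**Step 4. How many patients might be turned away.** The protocol gives no refusal rate, so r below is an assumption. To enrol 400, a site network needs 400 / (1 − r) otherwise eligible patients, rounded up. The excess over 400 is turned away.

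| Assumed refusal r | Eligible patients needed | Turned away |
|---|---|---|
| 5% | 422 | 22 |
| 10% | 445 | 45 |
| 20% | 500 | 100 |
| 30% | 572 | 172 |

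**Step 5. Effect of the fix on Cohort B.** All 3200 planned contacts belong to the 800 PTB households (step 2), so releasing EPTB adults and children from the rule removes none of them.

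**The case against.** The strongest reply is that household access has uses beyond Cohort B. Section 13 (Benefits to Subjects) promises screening of family members of Active TB Cohort participants generally. Section 6.2 collects socio-demographic data on all household members and a TB source evaluation from the index case. Section 9.1 plans Aim 1 models with household factors. A reader might infer that the exclusion serves no purpose at all for EPTB and paediatric cases, and these passages do not support that. They do not, however, show that consent to enrol contacts is needed from these patients. The only reason section 6.1 gives for disclosure is recruitment to Cohort B.

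Three other stronger readings also fail.

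- **Dilution of Aims 2 and 3.** A reader might infer that contacts of EPTB or child cases would enter Cohort B and weaken the exposure. The eligibility rule in section 5.2 still governs enrolment, and the analysis sets in section 9.1 are confined to PTB households.
- **A contradiction on consent within section 6.1.** Making the contact investigation depend on the index case's consent is redundant beside the exclusion but does not conflict with it. It keeps a meaning when a participant later withdraws, which section 13 allows.
- **A count of ineligible contacts approached.** Multiplying 400 cases by 4 contacts borrows the household size of PTB cases, and it ignores households that qualify through another member who is an adult PTB participant.

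It is also fair to say that a guardian consents for a child, so at least one adult in charge already knows the diagnosis. Selection on disclosure is therefore more plausible for the 200 EPTB adults than for the 200 children. No section reports a link between willingness to disclose and any outcome predictor.

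**Conclusion.** The mismatch is real. The exclusion, the disclosure request and the outreach instruction apply to all of Cohort A, while Cohort B is defined and sized only on contacts of adult PTB participants. As written, EPTB adults and children are excluded for declining consent to a cohort for which their case cannot be the index.

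The reach is 400 of 1200 planned participants. That figure is planned enrolment in the affected groups, not patients lost. The loss depends on a refusal rate that the protocol does not state. Selection on willingness to disclose is plausible but unmeasured, and it is confined to the secondary Aim 1 sets. The primary set of 800 adult PTB patients is unaffected, since there the rule does serve Cohort B. This assumes that the Cohort B definition, which the Protocol Summary and sections 4.3, 5.2 and 9.1 all share, is the intended one. If wider recruitment was meant, those sections need changing instead. The passages must be reconciled in either case. It should be corrected but does not threaten the primary analysis.

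**What to change.** 1. Limit exclusion vi in section 5.3, and the disclosure request in section 6.1, to adult PTB participants who are index cases for Cohort B.
2. In section 6.1 (Recruitment of Household Contact Cohort), limit the outreach team's approach to the adult PTB participants in the Active TB Cohort.
3. In the same edit, reconcile the home-visit requirement (section 5.2, item iii, and section 6.1) with that index population. Otherwise household-related selection of EPTB and paediatric cases continues by another route. Section 6.2 places all Cohort A assessments at the study clinic, so the reason for home visits to non-index participants should be stated or the requirement limited.
4. Align the family-screening statement in section 13 with the same population, or state that screening offered to other families is separate from Cohort B enrolment.

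The cost is wording in the protocol and the consent script. No planned contacts are lost. One small downside is that PTB and non-PTB participants would then enter under different consent conditions, which should be noted wherever the analysis sets are compared.
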